#### 6.4.2.3 Other Efficacy Variables

Other efficacy endpoints are:

- CBR according to RECIST v1.1, defined as the proportion of subjects with a BOR of CR, PR, or stable disease (SD).
- CBR according to the BOR definition which includes MR, defined as the proportion of subjects with a BOR of MR or better (i.e., CR, PR, SD, or MR).
- Time to progression defined as the time from first dose of study treatment until progression according to RECIST v1.1. Subjects without progression are censored at the date of the last evaluable tumor assessment. If a subject does not have any evaluable post-dose tumor assessments, they will be censored at the date of first dose plus 1 day.
- Progression free survival defined as the time from first dose of study treatment until progression according to RECIST v1.1 or death (whichever occurs first). Subjects without progression/death are right censored at the date of the last evaluable tumor assessment. If a subject does not have any evaluable post-dose tumor assessments, they will be censored at the date of first dose plus 1 day.
- Overall survival defined as the time from first dose of study treatment until death. Subjects without death are right censored at the date of last contact.

[REDACTED]

[REDACTED]

[REDACTED]

[REDACTED]

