### 7.5.1 Tumor Size

Tumor size will be determined using a suitable imaging technique, depending on the localization of the tumor. Computer tomography (CT) will preferably be selected. Radiology exams will be performed every 9th week ( $\pm 1$  week) post-treatment initiation (i.e., [REDACTED] [REDACTED]). However, at screening, if the patient has been subjected to radiology examination within 3 weeks prior to registration, this imaging can be used as baseline at the discretion of the Investigator. Definitions of measurable disease and response to treatment will follow RECIST 1.1 criteria. For research purposes, other methods such as immune-related (ir) RECIST may be compared to the RECIST v1.1 outcome. Further, a study-specific tumor evaluation will also be performed (see *“Instructions for lesion selection and effect evaluation”* provided by the Sponsor in the Investigator Site File).

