### **Progression-Free Survival (PFS)**

PFS is the time from start of the treatment to progression or death.

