## 6 INVESTIGATIONAL PLAN

### 6.1 Overall Study Design

This trial is a multicenter, open label, single arm, dose-escalation Phase I/II trial. The study will have a Bayesian Optimal Interval (BOIN) design ([Ying Yuan 2016](#)) with a target dose limiting toxicity (DLT) rate=0.3 to determine the maximum tolerated dose (MTD) of LOAd703 against a fixed dose of atezolizumab. This design has algorithmic escalation/de-escalation rules like a traditional 3+3 design, but it also allows for specification of the DLT target rate and expanded accrual beyond N=6 with continued and consistent toxicity monitoring. This means that the assessment of DLT rate continues throughout the study, giving a well-defined safety evaluation of the entire study.

[REDACTED]

The total number of subjects to be enrolled in the study to achieve at least 25 evaluable subjects at MTD, should not exceed 50.

[REDACTED]

The trial encompasses a treatment phase ending with last subject last visit (LSLV). For each subject, active participation with study visits is maximum 60 weeks where after they are followed for survival as long as the trial remains open.

After a screening period [REDACTED] each subject will receive a maximum of 12 LOAd703 injections (q3w) in combination with atezolizumab (q3w) after which supportive therapy with atezolizumab alone is continued until the final clinical visits (i.e., maximum 7 additional infusions).

The subjects will be scheduled for study visits until final clinical follow-up in study [REDACTED]. If both treatments are prematurely withdrawn the final clinical follow-up visit could be scheduled earlier, [REDACTED].

[REDACTED]

In total, subjects will visit the clinic regularly for a maximum 60 weeks [REDACTED]. Thereafter only OS will be recorded [REDACTED] whereby information will be collected via telephone calls (US) or medical records (Sweden, US) until death or study end.

The end of the treatment stage is defined as the date of the LSLV and the end of study is defined as LSLV.

The study is initially planned to be conducted at 2 sites in US and 1 site in Sweden. The study has been conducted in 3 sites in US and 1 site in Sweden.

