Before beginning the screening visit, the subject will be informed about the trial and sign informed consent whereupon the subject is enrolled in the trial. The subject will be evaluated for health status, pregnancy (if applicable) and tumor load (by appropriate radiological imaging). If the subject has been subjected to radiology examination within

three weeks prior to registration, this imaging can be reused for evaluation at the discretion of the Investigator. If all of the inclusion criteria and none of the exclusion criteria are met, the subject is registered to participate in the trial.

Appendix 1 (Schedule of Events) of the clinical study protocol shows the treatment schedule and timing of the study visits. Subjects will undergo 12 LOAd703 treatments (q3w) administered by i.t. injection until study [REDACTED]. Atezolizumab infusions (q3w) will continue during the study until progression or toxicity requires treatment discontinuation. On the day of the treatment, [REDACTED]

[REDACTED]

The treatments are scheduled on any of the designated study week working days. If the treatments are delayed to the next week, then they must be omitted in order to adhere to the protocol schedule.

Laboratory samples (toxicity, [REDACTED]

If both treatments are discontinued, a modified follow-up schedule will apply (see Appendix III of the protocol for further details).

During evaluation visits, the subject will be evaluated for health status, toxicity, and treatment effect on tumor size (radiology exam). Laboratory samples are taken for [REDACTED]. The final follow-up visit is scheduled at study [REDACTED].

If both LOAd703 and atezolizumab are discontinued (i.e., off-treatment subject), the subject should still be followed up and participate in the evaluation visits according to the Modified follow-up schedule, unless consent is withdrawn as well. Modified follow-up: subjects should complete visits [REDACTED] and after visit [REDACTED], the subjects will return for visits [REDACTED]

For off-treatment subjects, the final follow-up visit can be scheduled earlier but [REDACTED]

If another treatment is initiated due to progressive disease or other reasons, the subject will only be followed for survival (see Section 7.5.3 of the protocol: Survival Follow-Up). The final clinical follow-up visit ([REDACTED]) should then be scheduled to collect endpoint data ([REDACTED]) as close to the start of new treatment as possible.

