### 7.6.5.2 *Handling of Dropouts or Missing Data*

For the purpose of calculating time since initial melanoma diagnosis, partial diagnosis dates will be imputed as follows:

- Missing day only will be imputed with the 1st of the month;
- Missing day and month will be imputed with 1st January.

No imputation will be done if the diagnosis date is completely missing.

If the imputed date is after the date of informed consent, the date of informed consent will be used instead (i.e., a time since diagnosis will be computed as 1 day).

The analysis of TTP and PFS will censor subjects without events at the date of the last evaluable tumor assessment. If a subject does not have any evaluable post-dose tumor assessments, they will be censored at the date of first dose plus 1 day. The analysis of OS will censor subjects without events at the date of last contact.

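### PFS counts every late death but censors survivors at their last scan, so beyond the last scheduled scan the curve rests only on patients who later died and, if there is one, ends at zero

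*SAP*

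**What the plan says.** **Event.** SAP 6.4.2.3 starts PFS at first dose and ends it at RECIST v1.1 progression or death, whichever comes first. The protocol's definition is equally open-ended: "PFS is the time from start of the treatment to progression or death". Neither limits how long after the last scan a death may count.

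**Censoring.** SAP 6.4.2.3: "Subjects without progression/death are right censored at the date of the last evaluable tumor assessment". SAP 7.6.5.2 repeats it: "The analysis of TTP and PFS will censor subjects without events at the date of the last evaluable tumor assessment". For a patient with no evaluable post-dose scan and no event, "they will be censored at the date of first dose plus 1 day".

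**Follow-up.** Protocol 7.5.1: "Radiology exams will be performed every 9th week" (the exact weeks are redacted). SAP 6.1 limits clinic visits to 60 weeks and continues: "Thereafter only OS will be recorded". Scanning can stop sooner: "If another treatment is initiated due to progressive disease or other reasons, the subject will only be followed for survival". Deaths are still collected until the last patient's last visit (Protocol 7.5.3).

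**Reporting.** SAP 7.6.4 gives the 25th percentile, median and 75th percentile of PFS with 95% CIs, Kaplan-Meier plots, and estimates with numbers at risk every 3 months. It sets no upper time limit.

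**The concern.** Kaplan-Meier estimation needs the patients still at risk at a given time to represent everyone who is event-free at that time. Here, once scanning has ended, whether a patient is still at risk depends on the outcome. Take two patients with the same clean final scan. The one who dies at month 24 stays at risk until month 24 and is then an event. The one who is alive leaves at the final scan. The late risk set is selected on dying.

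At stake is the tail of the PFS curve, which is where a reader looks for durable benefit from an immunotherapy combination. A plateau of living, progression-free patients could be drawn as a fall to zero.

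**Working it through.** The documents give no planned PFS figure, so there is none to reproduce. The check has three parts.

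**1. Timeline**
- Last possible visit: 60 weeks = 420 days. With the SAP's month of 365.25/12 = 30.4375 days, 420/30.4375 = 13.8 months. The first 3-monthly estimate beyond any scheduled scan is the one at 15 months.
- Maximum time on study is 48 months (protocol synopsis). Read as the protocol's 4-week study months, this is 48 × 4 = 192 weeks.
- Period in which a death can enter PFS but no scan is planned: 192 − 60 = 132 weeks = 924 days, and 924/30.4375 = 30.4 months.

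**2. Kaplan-Meier by hand**

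Illustrative data: 25 patients, 17 with events by the last scan, 8 progression-free there. Of the 8, 3 die at 18, 22 and 26 months and 5 stay alive. Each step is S(new) = S(old) × (1 − deaths / at risk). The 5 survivors are censored at the last scan, so only 3 remain at risk.

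| Time | At risk | Deaths | S |
|---|---|---|---|
| Last scan | – | – | 8/25 = 0.320 |
| 18 months | 3 | 1 | 0.320 × 2/3 = 0.213 |
| 22 months | 2 | 1 | 0.213 × 1/2 = 0.107 |
| 26 months | 1 | 1 | 0.107 × 0 = 0 |

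- The 75th percentile (first time S ≤ 0.25) is 18 months. If the curve stopped at the last scan, it would stay at 0.32 and the 75th percentile would not be reached.
- One death is enough. With 10 of 25 progression-free (S = 0.40) and a single late death at 24 months, one patient is at risk and S goes from 0.40 to 0 while the other 9 are alive.
- With no late death, the curve stops at its plateau.
- The 75th percentile is exposed only if S is above 0.25 at the last scan: 7/25 = 0.28 is exposed, 6/25 = 0.24 is not.

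**3. Simulation (all inputs assumed; none is in the documents)**

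Set-up A: 30% never progress, the rest have a 4-month median to progression, 10-month median from progression to death, scans every 63 days to day 378, 28-month accrual, 42-month study, n = 25. The hazard of death without progression was varied.

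| Hazard per month | Trials in which the curve ends at 0 |
|---|---|
| 0 | about 63% |
| 0.4% | about 75% |
| 1.65% | about 90% |

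Over this range the true 30-month PFS is about 18–30%, against an estimate of 4–5%. With a 12-month median from progression to death, the three shares are 57%, 71% and 88%.

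Set-up B: scans at weeks 9 to 54, close at week 192, accrual over 130 weeks, 10% stop scans early, 0.4% per month hazard of death without progression, n = 25. It shows the direction of the error.
- 6-month median, 12-month median from progression to death, no plateau: estimated S(18 months) 0.178, true 0.117. The error is upward.
- 3-month median, 10-month median from progression to death, 20% never progressing: estimated S(24 months) 0.120, true 0.184. The error is downward.

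In every run of set-up B, everyone at risk after week 60 had a later recorded death.

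**The case against.** **Stronger readings that the documents do not support.**
- *The curve always collapses.* It does so only if at least one patient without documented progression dies after scanning has ended.
- *Everything after about 12 months is an artefact.* Visits run to 13.8 months. At 12 months, under set-up A's progression, accrual and scan schedule (1.65% per month, 12-month median from progression to death), the present rule and a rule that drops the late deaths both give 0.338. The first affected 3-monthly estimate is the one at 15 months.
- *PFS is always understated.* Early in the tail the error can go either way, as set-up B shows.
- *About nine trials in ten end at zero.* Under set-up A that needs a hazard of death without progression near 1.65% per month. Lower hazards give clearly lower shares.
- *TTP has the same fault.* It does not count deaths, so it does not.

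**The case for leaving the rule alone.** PFS is one of the SAP's other endpoints and is descriptive, with no formal dose comparison. TTP can already show a plateau, OS censors at last contact, and the printed numbers at risk would reveal a depleted tail. Parts of SAP 6.4.2.3 and 7.6.4 are redacted and could hold a further rule.

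**What stands.** These points limit the severity but do not cure the estimate. Printing the number at risk does not tell the reader that those patients are there because they died. The missing-data section, SAP 7.6.5.2, has readable TTP and PFS censoring text and contains no late-death rule.

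**Conclusion.** The point holds for the tail of PFS beyond the last scheduled scan. There the risk set consists only of patients with a later recorded death, and one such death forces the curve to 0. This follows from the SAP's wording and the visit schedule and needs no modelling assumption, except that no scan takes place after the last visit (none is planned).

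How often it would show does depend on assumptions: roughly 63–90% of 25-patient trials under set-up A. The damage is confined to the 3-monthly estimates from 15 months on, the end of the curve and, when more than 25% are progression-free at the last scan, the 75th percentile. Median PFS is largely unaffected; safety, ORR, TTP and OS are unaffected. Severity is minor.

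**What to change.** In SAP 6.4.2.3, 7.6.5.2 and 7.6.4, end the PFS analysis at the last scheduled tumour assessment, stated as one study week for all patients:
- Progression or death up to that time is an event.
- A patient whose only event is a death after that time is censored at the last evaluable assessment.
- No PFS percentile or 3-monthly estimate is reported beyond it.
- The present definition is kept as a labelled sensitivity analysis. OS keeps all deaths, and TTP needs no change.

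Deaths within the scan period stay events, including those after a switch to another therapy. Censoring them could be informative, because the switch may itself be due to progression. Some asymmetry therefore remains inside the scan period for patients whose scans stop early.

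**Cost.** A change of SAP wording and one programming rule, before database lock. A few late deaths leave PFS, including any soon after the final scan, and PFS is not estimated beyond about 14 months.

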## 6.5 Data Quality Assurance

Report summaries will be generated using validated Base SAS® software, version 9.4 or higher, on a PC or server-based platform. Additional validated software may be used to generate analyses, as needed.

All SAS programs that create outputs or supporting analysis datasets will be validated by a second statistical programmer or biostatistician. At a minimum, validation of programs will consist of a review of the program log, review of output or dataset format and structure, and independent confirmatory programming to verify output results or dataset content. Additionally, all outputs will undergo a review by a senior level team member before finalization.

The content of the source data will be reviewed on an ongoing basis by project statistical programmers and statisticians. Data will be checked for missing values, invalid records, and extreme outliers through defensive programming applications, analysis-based edit checks, and other programmatic testing procedures. All findings will be forwarded to the project data manager for appropriate action and resolution.

# 7 STATISTICAL METHODS

## 7.1 General Methodology

Data will be analyzed by Precision for Medicine biostatistics personnel. Statistical analyses will be reported with tables, figures, and listings, presented in rich text format, and using recommended ICH numbering. Output specifications for all tables, figures, and listings will be in conformance with guidelines specified by the ICH in Appendix 7 of the *Electronic Common Technical Document Specification* (Apr 2003).

### 7.1.1 Reporting Conventions

Baseline and safety tables will be summarized by dose group ( $1 \times 10^{11}$  VP LOAd703;  $5 \times 10^{11}$  VP LOAd703). Tables summarizing demographics and other baseline

characteristics will also include a column for all subjects combined (Total). Except where stated, efficacy tables and figures will be summarized for efficacy evaluable subjects by dose. In general, all data collected, and any derived data will be presented in subject data listings for all enrolled subjects. Listings will be ordered by dose group, subject number and assessment or event date. The dose group presented in listings will be based on the planned assignment, unless otherwise noted.

In general,

Non-zero percentages will be rounded to one decimal place. Rounding conventions for presentation of summary statistics will be based on the precision of the variable of summarization, as it is collected in its rawest form (i.e., on the eCRF or as provided within an external file) and are outlined as follows:

- [REDACTED]
- [REDACTED]
- [REDACTED]

Other statistics [REDACTED] will be presented using the same general rules outlined above or assessed for the most appropriate presentation based on the underlying data.

No formal statistical analysis will be performed to compare dose groups. Results will be presented with descriptive statistics will be tabulated by dose group and reviewed to evaluate all study endpoints.

### 7.1.2 *Summarization by Visit*

Data summarized by study visit will be based on the nominal, scheduled visit label as reported on the eCRF.

Data collected at unscheduled visits will not be included in by-visit summaries but will be considered when endpoint derivations potentially include multiple visits (e.g.,

determination of baseline value, determination of worst post-baseline value, etc.). All data will be included in subject listings.

### 7.1.3 Standard Calculations

Where appropriate, the calculated study day of each assessment or event will be presented with the assessment or event date on subject data listings, where study day will be determined as:

- The assessment/event date minus the date of first dose of study drug, if the assessment/event date is prior to the date of first dose; and
- The assessment/event date minus the date of first dose of study drug, plus one, if the assessment/event date is on or after the date of first dose.

Other variables requiring calculations will be derived using the following formulas:

- **Days:** A duration between two dates expressed in days will be calculated using the following conventions:
  - Later date – earlier date + 1, if the earlier date is on or after the date of first dose of study drug; or
  - Later date – earlier date, if the earlier date is prior to the date of first dose of study drug.
- **Months:** A duration expressed in months will be calculated by dividing the duration in days by (365.25 / 12);
- **Change from Baseline:** Change from baseline will be calculated as the post-baseline value minus the baseline value;
- **Percentage Change from Baseline:** Percentage change from baseline will be calculated as the change from baseline divided by the baseline value, multiplied by 100.

## 7.2 Analysis Populations

The analysis populations are defined as follows:

- Safety Population: [REDACTED]
- Efficacy Evaluable Population: [REDACTED]

Data summaries to be presented on both the Safety Population and the Efficacy Evaluable Population will only be produced on both analysis sets if there is a difference in the population groups.

Although not formal analysis populations, the following subgroups of subjects are also relevant:

- [REDACTED]
- [REDACTED]
- [REDACTED]

### 7.3 Study Subjects

#### 7.3.1 *Disposition of Subjects*

Subject disposition will be summarized for all enrolled subjects by dose group and over all subjects combined (total). Summaries will include the number and percentage of subjects in each analysis population, completing treatment, discontinuing treatment early by the primary reason for discontinuation, with Coronavirus Disease 2019 (COVID-19) as part of the reason for discontinuation of treatment, completing the study, discontinuing the study early by the primary reason for discontinuation and with COVID-19 as part of the reason for discontinuation of study. A by-subject listing will also be provided.

[REDACTED]

#### 7.3.2 *Protocol Deviations*

When all subjects have been completed, all data have been entered into the eCRF database, all coding is done and approved, and all queries are solved, the Database Closure procedures will begin. Decisions will be made on how to classify subjects into analysis populations, and how to handle protocol violations and deviating or missing data. All decisions will be dated and documented in a Database Closure document.

All protocol deviations will be listed, and major protocol deviations will be summarized by site (and for all sites combined), protocol deviation category, subcategory, and dose group and over all subjects combined (total).

#### 7.3.3 *Compliance with Study Schedule*

A listing showing compliance with the study schedule (i.e., including all visits that were performed or missed for each subject) will be provided.

## 7.4 Demographic and Other Baseline Characteristics

Demographic variables including age, sex, ethnicity, country, and race will be summarized by dose group and over all subjects combined (total) for the Safety and Efficacy Evaluable Populations and will be presented in a by-subject listing.

Age will be summarized using descriptive statistics. Sex, ethnicity, country, and race will be summarized with the number and percentage of subjects in each parameter category.

Baseline and disease characteristics including time from initial diagnosis (months), disease stage (at initial diagnosis and study entry), positive tumor-specific genetic markers\*, height, weight, body mass index (BMI), pregnancy test results and smoking status at Screening will be summarized for the Safety and Efficacy Evaluable Populations by dose group and over all subjects combined (total) and will be presented in by-subject listings.

BMI will be derived by the electronic data capture system as: weight (kg) / [height (cm) / 100].

Time from initial diagnosis (months) will be calculated as (Date of Informed Consent – Date of Initial Diagnosis + 1) / (365.25 / 12). Partial diagnosis dates will be imputed as per [Section 7.6.5.2](#).

[figure not shown]

Height, weight, and BMI at baseline and time from initial diagnosis will be summarized using descriptive statistics. Disease stage at initial diagnosis, disease stage at study entry, positive tumor-specific genetic markers, pregnancy test results and smoking status at Screening will be summarized by the number and percentage of subjects with each response.

Frequency counts and percentages to summarize subjects reporting relevant medical history by Medical Dictionary for Regulatory Activities (MedDRA, version 23.0) system organ class and preferred term will be presented for the Safety Population by dose group and over all subjects combined (total).

